9.5.3. Efficacy Analyses

The primary efficacy endpoint (SANDE) will be summarized using continuous summary statistics by treatment group and visit. The primary analysis will utilize a repeated measures mixed model where the dependent variable is the change from baseline score, treatment group is a fixed effect, baseline score is a covariate, and visit is a repeated measure on subject. The repeated measures mixed model is utilized to account for the effect of missing data under the assumption that the data are missing at random. Least squares means will be used to test SDP-4 to vehicle. Sensitivity analyses for the primary endpoint will be performed using last observation carried forward (LOCF) as well as observed data only.

The planned analyses for all efficacy outcomes will be described in detail in the SAP, which will be finalized prior to database lock.

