9.2. Determination of Sample Size

Based on results from SDP-4-CS201, a treatment difference of 12.2 units SANDE total score mean change from baseline at Day 56 was observed in the subgroup population meeting the Total SANDE score \geq 40 and \leq 70. A sample size of 70 subjects per treatment group will have 84.5% power to detect above observed treatment difference assuming observed standard deviations of the two groups (i.e., 22.7 and 25.4) using a two-sided t-test with a 0.05 significance level.

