9.5. Efficacy Endpoints and Analyses

9.5.1. Primary Efficacy Endpoint

Mean change from baseline in total SANDE score at Visit 5/Day 56

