5 EFFICACY

5.1 Efficacy Endpoints

- 5.1.1 Primary Efficacy Endpoint Mean change from baseline in total SANDE score at Visit 7/Day 84
- 5.1.2 Secondary Efficacy Endpoints
 - Mean and mean change from baseline at each visit for each of the following evaluations:
 - Conjunctival lissamine green staining (combined and each zone)
 - Corneal fluorescein staining (combined and each zone)
 - TBUT
 - Anesthetized Schirmer's test at Visit 7/Day 84
 - Conjunctival hyperemia
 - Individual symptom VAS scores, separately for each symptom
 - SANDE

 Mean and mean change from baseline in total SANDE score at each visit, excluding Visit 7/Day 84

 Mean and mean change from baseline in SANDE severity score at each visit

Mean and mean change from baseline in SANDE frequency score at each visit

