5.4 Methods of Efficacy Analysis

Each endpoint will be summarized for each visit where that endpoint is assessed. Where appropriate, the change from baseline value will be used to assess the difference between each concentration of SDP-4 and vehicle.

Change from baseline endpoints will be analyzed using MMRM analysis with terms for baseline measurement, treatment, visit, and treatment-by-visit interaction. An unstructured variance-covariance matrix will be employed to account for within subject correlation in the repeated measures. In case of model non-convergence a simpler variance-covariance matrix will be employed. Within treatment estimate of least square mean change from baseline and associated standard error will be provided by visit. Also, estimate of difference in least square means of change from baseline between each SDP-4 group and Vehicle (i.e. the estimand) and associated standard error and 95% confidence interval will be provided by visit.

The MMRM analysis is based on a standard linear mixed model, defined as:

$$Y = \mu + B_i + T_t + V_j + TV_{tj} + \underline{\varepsilon_{itj}}$$

Where **Y** denotes an outcome variable, μ is the overall mean, B_i is the baseline value, T_t is the fixed effect due to tth treatment group, V_j is the fixed effect due to the jth visit, TV_{tj} is the treatment by visit interaction, and $\underline{\varepsilon_{itj}}$ is the measurement error associated with the individual subject.

Following is a sample SAS code for MMRM analysis:

proc sort data=datain; by subject_id visit; ods select diffs lsmeans; proc mixed data=datain method=reml; class subject_id treat visit; model cfb_var= baseline treat visit visit*treat / solution rcorr; repeated visit / type=un subject=subject_id rcorr; lsmeans visit*treat / pdiff; run; guit;

For variables with only one post-baseline assessments (e.g. Schirmer's test), change from baseline will be analyzed utilizing analysis of covariance (ANCOVA) with terms for baseline measurement and treatment. The mathematical form of the ANCOVA model is also based on a standard linear mixed model, defined as:

$Y = \mu + B_i + T_t + \underline{\varepsilon_{it}}$

Where **Y** denotes an outcome variable, μ is the overall mean, B_i is the baseline value, T_t is the fixed effect due to tth treatment group, and $\underline{s_{it}}$ is the measurement error associated with the individual subject.

Following is a sample SAS code for ANCOVA analysis:

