8 CHANGES FROM PROTOCOL

- Following analyses have been removed from hierarchy of analyses as described in protocol Section 9.5.3 Efficacy analysis:
 - Secondary (TBUT) high concentration vs. vehicle
 - Secondary (TBUT) middle concentration vs. vehicle
 - Secondary (TBUT) low concentration vs. vehicle
- IP comfort assessment has been disregarded as one of the safety assessments.

Downloaded by [name] on 4/29/2020

REFERENCES

None

Statistical Analysis Plan: Final Version 1.0, 24 June 2019

Downloaded by [name] on 4/29/2020

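### Read as written, the protocol's primary mixed model has no visit or treatment-by-visit effect, so it tests a pooled Day 14/28/56 difference instead of the Day 56 endpoint

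*Protocol*

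**What the plan says.** Protocol 9.5.1 defines the primary endpoint at a single visit: "Mean change from baseline in total SANDE score at Visit 5/Day 56". The sample size in 9.2 is tied to the same day: "a treatment difference of 12.2 units SANDE total score mean change from baseline at Day 56 was observed in the subgroup population". It uses SDs of 22.7 and 25.4, 70 subjects per group and a two-sided 0.05 t-test, with a stated power of 84.5%.

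Section 9.5.3 gives the primary analysis as a repeated measures mixed model on change from baseline, in which "treatment group is a fixed effect, baseline score is a covariate, and visit is a repeated measure on subject". The comparison is then stated as "Least squares means will be used to test SDP-4 to vehicle". No visit is attached to those means. The protocol lists no visit fixed effect or treatment-by-visit term anywhere, and 9.5.3 names no covariance structure. It leaves the detail for later: "The planned analyses for all efficacy outcomes will be described in detail in the SAP".

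The supplied SAP (section 5.4) specifies "MMRM analysis with terms for baseline measurement, treatment, visit, and treatment-by-visit interaction", with an unstructured covariance matrix and by-visit differences. Its primary endpoint (5.1.1) is "Mean change from baseline in total SANDE score at Visit 7/Day 84", and its design (1.2) has four arms treated for 12 weeks. Its date line reads "Statistical Analysis Plan: Final Version 1.0, 24 June 2019", whereas the protocol is dated 06 March 2020.

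**The concern.** Section 9.5.3 assigns each model term a role, and visit's only role is to index the repeated measurements. A mean model with one treatment coefficient yields one treatment difference for all three post-baseline visits. That quantity is neither the endpoint in 9.5.1 nor the one powered in 9.2.

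The consequence depends on how the effect develops. If it builds over 8 weeks, the smaller early differences dilute the primary test. If it appears early and fades, the trial can succeed with no Day 56 effect. If it is flat, the pooled test has more power than planned. If the wording is only shorthand, the contrast that decides the trial is still not written down, and two analysts could report different primary p-values from the same data.

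**Working it through.** **1. Inputs from the documents.** Day 56 difference 12.2; SDs 22.7 and 25.4; 70 per group; two-sided alpha 0.05 (Protocol 9.2). Post-baseline visits at Days 14, 28 and 56 (Protocol 3.1).

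**2. The plan's own figure.** Pooled SD = √((22.7² + 25.4²)/2) = 24.09. SE of the Day 56 difference = 24.09 × √(2/70) = 4.07. Noncentrality = 12.2/4.07 = 3.00. With 138 degrees of freedom the noncentral t gives 84.5%, matching the protocol. The power statement is therefore for a Day 56 comparison.

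**3. What the literal model estimates.** Let V be the 3 × 3 within-subject covariance matrix over the three visits and **1** a vector of ones. With complete data and a treatment effect common to all visits, the generalised least squares estimate is a weighted mean of the visit differences:

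- weights w = V⁻¹**1** / (**1**ᵀV⁻¹**1**)
- SE = √(2 / (n **1**ᵀV⁻¹**1**))

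It equals the Day 56 difference for every V only when the effect is the same at all visits.

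**4. Assumptions needed for a size.** None of these is in the documents: the time course of the effect, equal SDs of 24.09 at each visit, compound symmetry with correlation ρ of 0.3, 0.5 or 0.7, no dropout, and no gain from baseline adjustment. The weights are then 1/3 each, and SE = 24.09 × √(2(1 + 2ρ)/(3 × 70)), which is 2.97, 3.32 and 3.64.

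| Effect at Days 14/28/56 | Pooled estimate | Pooled test significant, ρ = 0.3/0.5/0.7 | Day 56 t-test significant |
|---|---|---|---|
| 3.05/6.1/12.2 | (3.05 + 6.1 + 12.2)/3 = 7.1 | 66/57/49% | 84.5% |
| 4/8/12.2 | (4 + 8 + 12.2)/3 = 8.1 | 77/67/60% | 84.5% |
| 8/4/0 | (8 + 4 + 0)/3 = 4.0 | 27/22/19% | 5% |
| 12.2/12.2/12.2 | 12.2 | 98/95/91% | 84.5% |

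**5. Dependence on the covariance.**

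- AR(1) by visit order, equal SDs: the Day 56 weight is 0.37 to 0.43, and the 3.05/6.1/12.2 course has 72% to 56% power.
- SDs rising 16/20/24 with compound symmetry: the Day 56 weight is 0.14, 0.06 and -0.11 at ρ = 0.3, 0.5 and 0.7. At ρ = 0.3 the 3.05/6.1/12.2 course gives an estimate of 5.2 and 61% power, 8/4/0 is significant 68% of the time, and a flat 12.2 has over 99% power.

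**6. Simulation check.** Fitting a treatment-only mean with an estimated unstructured covariance (equal SDs, 3000 runs per scenario, ρ = 0.3/0.5/0.7) gave 67/57/50% for 3.05/6.1/12.2, 27/22/21% for 8/4/0 and 98/96/91% for the flat effect. With no effect at any visit it rejected 4.4/5.4/5.2% of the time, so this is a mismatch of target and not type I error inflation under a global null. A time trend common to both arms changed little.

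**7. With the visit terms added.** In a separate simulation (400 runs per scenario, ρ = 0.5), the Day 56 contrast averaged 12.0 to 12.7 for a true 12.2, with 82% to 87% power. It rejected about 5% of the time when the Day 56 difference was zero.

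**The case against.** The strongest reply is that 9.5.3 is a summary and that calling visit a repeated measure is ordinary shorthand for an MMRM with visit terms. Several things support this. Section 9.5.1 already fixes the visit for the primary endpoint. Section 9.5.2 asks for SANDE change at every visit, which a treatment-only mean cannot supply. The LOCF and observed-data sensitivity analyses fit a Day 56 comparison most naturally. The supplied SAP lists exactly the missing terms and states that it supersedes the protocol's statistical considerations. On this view the real gap is the lack of a SAP matching this protocol, and the missing terms follow from that gap.

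Much of this stands. The shorthand reading is plausible, and nothing shows that the sponsor intends a pooled test. The numerical results illustrate a mechanism under invented time courses, can go either way, and span a wide range. But the SAP cannot settle the matter. It predates the protocol, cites a protocol amendment of 03APR2019, and places its primary contrast at a visit this trial does not have. No supplied document states a Day 56 primary contrast for the two-arm trial, and the model that is stated does not deliver one.

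**Conclusion.** The concern holds for the protocol as written: the stated model targets a covariance-weighted average over Days 14, 28 and 56, while the endpoint and the 84.5% power are for Day 56. That follows from the model's form and needs no assumption about the drug. It does not establish that the sponsor would actually run a pooled test. The size does rest on assumptions. With equal SDs and compound symmetry, the two building effects above have 49% to 77% power, against 84.5% at Day 56, and a flat effect has 91% to 98%. Dropout was not modelled, and nothing is claimed about missing data. This should be fixed before database lock.

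**What to change.** In Protocol 9.5.3, and in a SAP written for this two-arm, 8-week trial, list treatment, visit and treatment-by-visit as fixed effects with baseline as covariate. Name the covariance structure, for example unstructured, with a stated fallback if the model does not converge. Declare the Day 56 SDP-4 minus vehicle LS-mean difference as the single primary test. A baseline-by-visit term and Kenward-Roger degrees of freedom are optional refinements.

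The cost is a wording change and a few model degrees of freedom, with no new data or subjects. The real trade-off is power if the effect is flat across visits: 84.5% for the Day 56 test, against 91% to 98% for a pooled test under equal-SD compound symmetry and over 99% if SDs rise over time. If the sponsor prefers an average over visits, the endpoint and the sample size statement should be rewritten to match.

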9.6. Safety Variables and Analysis

9.6.1. Safety Variables

Safety variables are as follows:

- Ocular and non-ocular AE monitoring
- BCVA
- Biomicroscopy
- IP comfort assessment

9.6.2. Safety Analysis

Safety and IP comfort data will be presented in tables of descriptive statistics and frequency distribution. All summary tables will be supported with individual subject data listings.

AEs that occur during the screening/run-in period (Visit 1/Day-14 \pm 2 to Visit 2/Day 1) will be summarized separately from AEs that occur from the first dose of double-masked treatment on Day 1 to the Day 56 Visit or Early Discontinuation.

The primary safety analysis will summarize ocular and non-ocular treatment-emergent adverse events (TEAEs) using discrete summaries at the subject level by system organ class and preferred term for each treatment group. A TEAE will be defined as occurring after the first dose of IP. Serious adverse events (SAEs) and treatment-related ocular and non-ocular TEAEs will be summarized similarly. Ocular and non-ocular TEAEs will also be summarized by severity.

Biomicroscopy and dilated indirect ophthalmoscopy measures will be summarized by tabulating the distribution of score shifts between baseline and post-baseline assessments

Best-corrected visual acuity (BCVA; logMAR) will be summarized at each visit, using continuous and discrete summary statistics, including change from baseline and the proportion of study eyes with pre-defined increases from baseline, specifically, eyes with a 3-line decrease in BCVA.

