3. INVESTIGATIONAL PLAN

3.1. Overall Study Design and Plan

This is a Phase 2, multicenter, double-masked, randomized, vehicle-controlled, doseresponse, parallel-group study designed to evaluate the safety and efficacy of SDP-4 ophthalmic solution in subjects with moderate to severe DED in both eyes (OU) over an 8week (56-day) treatment period.

Subjects will be randomized to 1.0% SDP-4 Ophthalmic Solution or vehicle in a 1:1 ratio in parallel groups. All investigational product (IP) (SDP-4 and vehicle) will be provided in single-use dose (SUD) containers packed in sealed foil pouches. Subjects, the Investigator, and all site personnel responsible for performing study assessments will remain masked to treatment assignment.

The IP will be administered via topical ocular instillation, one drop per eye, twice daily (BID) for 8 weeks (56 days). Both eyes will be treated with the same SUD at each dosing period. A 2-week screening/run-in period on BID vehicle will precede the 8-week randomized treatment period.

Subjects must have a Symptom Assessment in Dry Eye (SANDE) total score of \geq 40 and \leq 70 at Visit 1/Screening and Visit 2/Day 1 to enter the trial. For subjects with a qualifying SANDE score who meet all other inclusion/exclusion criteria, the eye with the lower tear break-up time (TBUT) at Visit 2/Day 1 will be designated as the study eye. In the event both eyes have the same TBUT scores, the eye with the lower Schirmer's test score at Visit 1 will be designated as the study eye. If both eyes have the same TBUT and Schirmer's test scores, the right eye will be designated as the study eye.

The study will consist of 5 clinic visits, 2 visits during the screening period and 3 on-treatment visits: Visit 1 (Day -14 ± 2 /Screening Visit), followed by the 2-week run-in period on BID vehicle, Visit 2 (Day 1/Confirmatory and Baseline/Randomization Visit), Visit 3 (Day 14 ± 2), Visit 4 (Day 28 ± 2), and Visit 5 (Day 56 ± 4 /End of Study Assessments).

See Table 1, Schedule of Visits and Examinations.

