6.8. Other Safety Assessments

6.8.1. Best-Corrected Visual Acuity

Best-corrected visual acuity (BCVA) measurement will be performed in each eye at all study visits with the logMAR eye chart using the subject's best corrective lens prescription eyeglasses or trial frame lenses, if applicable. The subject's BCVA must be determined (via refraction) if corrected or uncorrected visual acuity is not logMAR 0.0 (equivalent to 20/20). This refraction must be used for all VA assessments for the duration of the study. The subject must wear the same glasses/trial frame, if applicable, at each visit. Ambient room lighting should be consistent for a given subject throughout the study period. Consult the Study Reference Manual for specific details regarding the evaluation procedures.

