9. STATISTICS

9.1. General Considerations

This is a Phase 2, multicenter, randomized, double-masked, vehicle-controlled, parallel group study to evaluate the safety and efficacy of 1.0% SDP-4 ophthalmic solution in subjects with DED.

Subjects with DED are planned to be randomized to SDP-4 (1.0%) or vehicle in a 1:1 ratio, with 70 subjects randomized to each group.

A biostatistician will perform statistical analyses as agreed with the Sponsor according to the Statistical Analysis Plan (SAP).

All continuous study assessments will be summarized by treatment and visit (as applicable) using descriptive statistics (n, mean, median, standard deviation, minimum, and maximum). All categorical study assessments will be summarized by treatment and visit (as applicable) using frequency counts and percentages.

All study data will be listed by treatment, subject, and visit (as applicable).

The unit of analysis for efficacy will be the study eye.

Efficacy analysis will be conducted on the intent-to-treat (ITT) population (primary efficacy analysis) and the per protocol (PP) population (secondary efficacy analysis). Safety analyses will be performed using the safety analysis population. Definitions for the analysis populations may be found in Section 9.3.

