6.2 Visual Acuity

Descriptive statistics of the observed and change from baseline BCVA expressed as equivalent logMAR will be tabulated for each eye (study eye and non-study eye) by visit. In addition, the number and percentage of subjects with $a \ge 3$ -line decrease from baseline in BCVA will be tabulated for each eye (study eye and non-study eye) by visit and at any visit.

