6.4 Slit-Lamp Examination

Observed results will be summarized for each anterior ocular structure (Lid, Conjunctiva, Cornea, Anterior chamber, Iris/Pupil, Lens status) in frequency tables for each eye (study eye and non-study eye) by visit.

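### Protocol 9.6.2 counts 3-line vision loss in study eyes only, although both eyes are dosed and measured; SAP 6.2 counts both eyes but was not written for this trial

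*Protocol*

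**What the plan says.** Protocol 9.6.2 (Safety Analysis) promises continuous and discrete summaries of BCVA, including "the proportion of study eyes with pre-defined increases from baseline, specifically, eyes with a 3-line decrease in BCVA". The mixed direction is presumably logMAR, where a higher value means worse acuity. The restriction to study eyes is explicit.

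Other parts of the protocol bear on it:

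- Section 3.1: "Both eyes will be treated with the same SUD at each dosing period".
- Section 6.8.1: "Best-corrected visual acuity (BCVA) measurement will be performed in each eye at all study visits".
- Section 3.1, on how the study eye is chosen: "the eye with the lower tear break-up time (TBUT) at Visit 2/Day 1 will be designated as the study eye". Ties go to the lower Schirmer score, then to the right eye.
- Section 9.1: "The unit of analysis for efficacy will be the study eye". No matching statement is made for safety.
- Section 6.6 advises investigators to consider recording a loss of 3 lines or more as an AE, without limiting this to one eye.

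SAP 6.2 handles the same outcome differently. The count of subjects losing at least 3 lines "will be tabulated for each eye (study eye and non-study eye) by visit and at any visit", and SAP Table 14.3.3.4 is reserved for categorised change in the non-study eye.

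**The concern.** Safety is part of the primary objective (Protocol 2.1). The study eye is picked on baseline tear film, not on exposure: the fellow eye gets the same drops from the same vial for the same 56 days. Designating one eye makes sense for efficacy, and the protocol confines it to efficacy in Section 9.1. Section 9.6.2 then carries it into a safety count without giving a reason.

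What is at stake is a rare event in small arms. With 70 subjects per group, a between-arm tabulation of marked vision loss will hold very few cases, and one or two omitted cases can change how the table reads. The threshold is also loose. Section 9.6.2 speaks of a 3-line decrease, while Protocol 6.6 and SAP 6.2 both make clear that larger losses count.

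**Working it through.** The plan gives no figure on this point to reproduce, so the check is a comparison of texts followed by an illustration.

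**Comparison of texts**

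| Item | Protocol 9.6.2 | SAP 6.2 |
|---|---|---|
| Eyes in the 3-line count | Study eye | Study eye and non-study eye |
| Threshold | A 3-line decrease | 3 or more lines |
| Timing | BCVA summarised at each visit | By visit and at any visit |
| Either-eye (subject-level) count | None | None |

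**Does the SAP settle the conflict?** SAP Section 1 says that it takes precedence over the protocol's statistical text. The protocol it names, however, carries an Amendment 1 dated 03APR2019.

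| Feature | Supplied SAP | This protocol |
|---|---|---|
| Arms | 0.1%, 1.0%, 3.0% and vehicle | 1.0% and vehicle |
| Subjects per group | 75 | 70 |
| Treatment period | 84 days | 56 days |
| Date | 24 June 2019 | 06 March 2020 |

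Protocol Section 1 describes an earlier Phase II study of the same three concentrations, which matches the SAP's design. Protocol 9.5.3 also says a SAP will be finalised before database lock. The precedence clause therefore cannot be assumed to reach this trial.

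**Illustration of size.** The inputs are n = 70 per arm (Protocol 9.2), an assumed per-eye risk q = 0.01, and an assumed between-eye correlation ρ from 0 to 1. The documents give neither q nor ρ.

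- Both eyes affected: q² + ρq(1 − q)
- Either eye affected: 2q − P(both)
- Fellow eye only: q − P(both)
- Share missed by a study-eye count: P(fellow only) / P(either)
- At least one case among 70: 1 − (1 − p)^70

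For study eyes only, 1 − 0.99^70 = 0.505, whatever the correlation.

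Worked case at ρ = 0.3: P(both) = 0.0001 + 0.3 × 0.0099 = 0.00307. P(either) = 0.02 − 0.00307 = 0.01693. P(fellow only) = 0.01 − 0.00307 = 0.00693. Share missed = 0.00693 / 0.01693 = 0.41.

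| ρ | P(either eye) | At least one case, either eye | Share of affected subjects missed |
|---|---|---|---|
| 0 | 0.0199 | 75.5% | 50% |
| 0.3 | 0.0169 | 69.7% | 41% |
| 0.6 | 0.0140 | 62.6% | 28% |
| 1 | 0.0100 | 50.5% | 0% |

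The share missed hardly depends on q: at q = 0.05 it is 49%, 40%, 28% and 0% for the same correlations. The number of subjects does depend on q. At q = 0.02 and ρ = 0.3, about 70 × 0.0337 = 2.4 subjects per arm are affected in some eye, 70 × 0.02 = 1.4 are counted, and 70 × 0.0137 = 1.0 is affected in the fellow eye only.

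These are chances of seeing a case. They are not power to detect a difference between arms.

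**The case against.** The strongest reply is that SAP 6.2 and Table 14.3.3.4 already put fellow-eye losses in a safety table, and that the SAP claims precedence. This would be decisive if the SAP belonged to CS202. On its own description it does not, so the reply shows how easily the gap can be closed but not that it is closed. Even under SAP 6.2 there is no either-eye row, although SAP Section 6 makes the subject the unit for all safety variables and promises subject-level data for eye-specific ones.

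The second reply is that one restricted proportion is not the whole safety evaluation. This stands. A reader might infer that a fellow-eye loss vanishes from the safety results, or that half of the exposed eyes are discarded. The documents do not support that:

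- The primary safety analysis in 9.6.2 is subject-level ocular and non-ocular TEAEs, with no eye restriction.
- The wording on BCVA summaries is inclusive rather than exhaustive, and the continuous summary names no eye.
- Individual data are listed.

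These routes soften the gap without replacing the count. AE recording of a 3-line loss is only something to consider, and listings do not tabulate one arm against the other.

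The third reply is that the two eyes share a vial and a product, so their outcomes may be strongly correlated and few cases would be fellow-eye only. This is possible, and it is why the range runs down to 0%.

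A reader might also charge the SAP with silently replacing the protocol's biomicroscopy shift tables by frequencies per visit (SAP 6.4: "Observed results will be summarized for each anterior ocular structure"). That does not hold. Section 8 of the SAP lists departures from a different protocol, which is not supplied, so its silence proves nothing. Protocol 9.6.2 itself already specifies shift summaries and sets no eye restriction on them.

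**Conclusion.** The point holds in a limited form. The 3-line proportion in Protocol 9.6.2 leaves out a loss confined to the fellow eye, with no stated reason, although that eye is dosed and measured on the same schedule. The supplied SAP says something different, but it describes another design and predates this protocol, so the conflict is unresolved.

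The textual finding rests on no assumption. Its size does: under an assumed 1% per-eye risk and 70 subjects, a study-eye count misses between none and half of affected subjects, depending entirely on a between-eye correlation that the documents do not give. The effect is limited to one categorical summary. It does not show that fellow-eye harm would go unseen, and it does not touch the efficacy analysis.

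**What to change.** In Protocol 9.6.2, and in a SAP written for CS202, tabulate the number and percentage with a loss of 3 or more lines from baseline for (a) the study eye, (b) the fellow eye and (c) either eye, counted once per subject, by visit and at any visit. State the threshold as 3 or more lines in both documents. When the CS202 SAP is written, carry over the biomicroscopy shift-from-baseline summaries that the protocol already specifies.

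The cost is one change of wording and a few extra table rows. BCVA is already collected in each eye at every visit, so no new assessments or subjects are needed.
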